#### 2.8.4.2 ECG and cardiac imaging data

Data on ECG will be summarized descriptively by treatment group and visit.

Any significant findings will be documented as AEs and reported as such.

#### 2.8.4.3 Vital signs

Data on Vital Signs will be summarized descriptively by treatment group and visit.

Any significant findings will be documented as AEs and reported as such

#### 2.9 Pharmacokinetic endpoints

Not applicable.

#### 2.10 PD and PK/PD analyses

Not applicable.

#### 2.11 Patient-reported outcomes

Descriptive statistics will be provided for the FACIT and the SF-36V2 questionnaire including absolute change from baseline up to the end of study for the FAS.

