12.8 Sample size calculation

12.8.1 Primary endpoint

This trial is intended to estimate the difference in the rates of patients achieving a sustained response off treatment at Week 52.

(sustained response off treatment = maintain platelet $\geq 30 \times 10^9/L$ after treatment discontinuation in the absence of bleeding events \geq Grade II or use of any rescue medication at all visits until Week 52)

The sample size calculation is based on the following assumptions:

- 1. Sustained response off treatment is achieved in 30% of the patients in the dexamethasone arm and 65% in the eltrombopag + dexamethasone arm
- 2. Randomization is allocated in a 1:1 ratio (eltrombopag + dexamethasone: dexamethasone)
- 4. A two-sided 5% level of significance will be applied.
- 5. The study will have 90% power under the stated assumptions for the primary endpoint.

Based on these assumptions, a total of 47 patients in each treatment arm would need to be randomized. More conservative scenarios based on lower treatment effects and 50 patients per group, assuming rates of 30 versus 60% would lead to a power of 81%, and 30 versus 55% would still allow for a power of 64%, whereas the radius of the respective confidence interval would be between 0.20 and 0.21 based these scenarios.

To allow for some dropouts / protocol violations, a total of 106 patients is planned to be enrolled.

Due to feasibility reasons, resulting in a substantial delay in recruitment, as described above, with Amendment 3 recruitment will be prematurely discontinued. A final number of ca. 24 patients is expected to be recruited by the time of approval.

The patients enrolled by then will be analyzed and reported as described, to allow for adequate use of the present data.

Based on the assumptions described, the resulting power will be ca. 24%. As a consequence, all analyses will be performed in a purely descriptive manner.

13 Ethical considerations and administrative procedures

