### 1.1 Study design

This is a Phase II, multicenter, randomized (1:1), open-label study to compare the efficacy and safety of eltrombopag in combination with a short course of high-dose dexamethasone to 1-3 cycles of high-dose dexamethasone monotherapy, as first-line treatment in adult patients with newly diagnosed immune thrombocytopenia (ITP).

Randomization to treatment will follow a 1:1 ratio. No stratification is applied. A total of n=106 will be enrolled.

No interim analysis is planned. The analysis will be performed once all patients completed their final visits or terminated the study prematurely.

Objectives		Endpoints		
Primary Objective		Endpoint for primary objective		
1.	To compare the ability of eltrombopag in combination with a short course of dexamethasone to induce a sustained response off treatment at 52 weeks versus a defined course of dexamethasone	
 
Rates of patients achieving a sustained response off treatment at 52 weeks, comparing the two arms         (sustained response off treatment = maintain platelet count ≥ 30 × 10^9/L after treatment discontinuation in the absence of bleeding events ≥ Grade II or use of any rescue medication at all visits until Week 52)
 
		
Se	econdary Objectives	Endpoints for secondary objectives		
1.	To compare the ability of eltrombopag in combination with a short course of dexamethasone to induce overall response (OR) after treatment discontinuation at Week 52 versus a defined course of dexamethasone	
 
Proportion of patients with platelet count         ≥ 30 × 10^9/L and ≥ 2-fold increase of screening         platelets after treatment discontinuation in the         absence of bleeding events ≥ Grade II and no         rescue therapy at all visits until Week 52     
 
		
2.	To assess the duration of sustained response off treatment	
 
Median duration of sustained response off treatment calculated from the time of treatment discontinuation until platelet count < 30 × 10^9/L or bleeding events ≥ Grade II or use of any rescue therapy
 
		
3.	To assess the ability of eltrombopag to induce overall response (OR) by Week 4	
 
Proportion of patients with platelet count         ≥ 30 × 10^9/L and ≥ 2-fold increase of screening         platelet count and absence of bleeding and no         rescue therapy at least once by Week 4     
 
		

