# 3 Sample size calculation

This trial is intended to estimate the difference in the rates of patients achieving a sustained response off treatment at Week 52.

The sample size calculation is based on the following assumptions:

- 1. Sustained response off treatment is achieved in 30% of the patients in the dexamethasone arm and 65% in the eltrombopag + dexamethasone arm
- 2. Randomization is allocated in a 1:1 ratio (eltrombopag + dexamethasone: dexamethasone)
- 4. A two-sided 5% level of significance will be applied.
- 5. The study will have 90% power under the stated assumptions for the primary endpoint.

Based on these assumptions, a total of 47 patients in each treatment arm would need to be randomized. More conservative scenarios based on lower treatment effects and 50 patients per group, assuming rates of 30 versus 60% would lead to a power of 81%, and 30 versus 55% would still allow for a power of 64%, whereas the radius of the respective confidence interval would be between 0.20 and 0.21 based these scenarios.

To allow for some dropouts/protocol violations, a total of 106 patients is planned to be enrolled.

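### FACIT-Fatigue and SF-36v2 are summarised as change from baseline, but no between-arm estimate adjusted for the baseline score is planned, and about 12 unstratified patients per arm leave room for sizeable chance imbalance

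*SAP*

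**What the plan says.** Health-related quality of life is secondary objective 8 in both documents. Protocol 8.5.1 has both questionnaires completed before any study drug is given and again after 1, 2, 4, 12, 26 and 52 weeks. SAP 2.11 and protocol 12.5.4, in the same words, plan descriptive statistics for the FAS "including absolute change from baseline up to the end of study for the FAS". SAP 2.7.1 item 8 adds the visits and mentions domain and total scores. None of these places names a between-arm difference, a confidence interval or a model containing the baseline score. Section 2.11 does not say that the summaries are by arm; I take that as intended in a two-arm trial.

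Three other places bear on the point:
- SAP 2.1 gives the summaries for any continuous variable: number, mean, SD, minimum, median and maximum.
- SAP 2.7.1 and 2.7.2 say that secondary parameters are analysed like the primary parameter or its supportive analyses. The primary model in SAP 2.5.2 is a logistic regression with pre-therapy, screening platelet count and age as cofactors.
- Protocol 8.5.1 also announces an evaluation of a minimal clinically important difference for FACIT-Fatigue, without a threshold or method. The SAP does not take it up.

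On design, SAP 1.1 states "No stratification is applied". On size, protocol 12.8.1 first says "a total of 106 patients is planned to be enrolled" and then, after Amendment 3, "A final number of ca. 24 patients is expected to be recruited by the time of approval". The SAP still carries 106.

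**The concern.** In a two-arm randomised trial, readers will compare the arms on quality of life whether or not the objective is worded as a comparison. The natural contrast from the planned output is the difference in mean change. A change score subtracts the whole baseline value, which is more than the correlation between baseline and follow-up justifies. The arm that happens to start worse therefore tends to show the larger improvement through regression to the mean.

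At the planned size this would have been minor. At about 12 per arm the chance baseline difference is roughly twice as large, and the text on patient-reported outcomes was not revisited when recruitment was stopped. At stake are the readability and precision of a secondary result. The primary endpoint and the safety analyses are not affected.

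**Working it through.** **The plan's own figures.** No figure is stated for the questionnaires, so the check starts with the sample size. The inputs are 30% versus 65%, 1:1 allocation, two-sided 5% and 90% power (SAP 3, protocol 12.8.1). The continuity-corrected two-proportion formula gives 47 per arm, as stated (41 without the correction). The corresponding power at 12 per arm is 24.3%, against the stated figure of about 24%. About 12 per arm is thus the protocol's own working size.

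**Inputs for this point.** n = 12 per arm, from 24/2. The documents give neither the SD of the scores nor the baseline-to-follow-up correlation ρ. Results are therefore in units of the between-patient SD, taken as equal at both times and in both arms, with ρ assumed between 0.3 and 0.9. Every patient is assumed to have both values.

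**Chance baseline imbalance.** The difference in baseline means, D, has mean zero and standard deviation √(2/n).
- n = 12: √(2/12) = 0.41 SD, 95% range ±0.80 SD; the chance of exceeding 0.5 SD in either direction is 22%.
- n = 53 (106/2): √(2/53) = 0.19 SD, ±0.38 SD; the same chance is 1%.

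**What enters the raw-change contrast.** Given D, the expected difference in change is displaced by −(1−ρ)D. Over repeated randomisations this has mean zero and standard deviation (1−ρ) × 0.41.

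**Variance.** All entries share the factor 2/n.
- Raw change: 2(1−ρ).
- Baseline-adjusted: 1−ρ², times 1 + 1/(2n−4) = 1.05 as a small-sample allowance.
- Ratio of adjusted to raw: 1.05 × (1+ρ)/2.

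| ρ (assumed) | SD of chance component | SE, raw change | SE, adjusted | Variance ratio | Reduction |
|---|---|---|---|---|---|
| 0.3 | 0.29 | 0.48 | 0.40 | 0.68 | 32% |
| 0.5 | 0.20 | 0.41 | 0.36 | 0.79 | 21% |
| 0.7 | 0.12 | 0.32 | 0.30 | 0.89 | 11% |
| 0.8 | 0.08 | 0.26 | 0.25 | 0.945 | about 5% |

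At ρ = 0.9 the ratio is 1.05 × 0.95 = 0.9975, so the gain is practically nil.

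**The chance component is not an extra error.** (1−ρ)² + (1−ρ²) = 2(1−ρ). The first term is the variance from baseline imbalance and the total is the raw-change variance, both before the factor 2/n. At ρ = 0.5 this reads 0.25 + 0.75 = 1.00. The raw-change SE thus already contains the imbalance; adjustment removes that term and pays the 5% allowance.

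**In usable terms.** The 95% CI half-width falls from about 1.00, 0.85 and 0.66 SD to 0.83, 0.75 and 0.62 SD at ρ = 0.3, 0.5 and 0.7.

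**The case against.** The strongest reply is that no comparison was promised. The primary objective and secondary objective 1 are worded as comparisons; objective 8 is worded as an evaluation, with change in scores as its endpoint, and the plan delivers that. Amendment 3 made every analysis purely descriptive, and a table of model-based intervals invites readers to look for those that exclude zero. This stands as a reason to keep the addition descriptive. It does not rule it out: SAP 2.5.2 still reports a covariate-adjusted odds ratio with a confidence interval and p-value for the primary endpoint, and the request here is for less.

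A reader might infer that baseline scores serve only to form change, and that one can do no more than subtract two raw mean changes. The text does not support this. Change is included among the descriptive statistics, and SAP 2.1 provides number, mean and SD. With those by arm, an imbalance could be seen and an unadjusted difference with its interval worked out. What cannot be recovered from such summaries is the baseline-adjusted estimate.

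One might also think that SAP 2.7.1 and 2.7.2 fill the gap. They lead to a logistic model for a binary response without a baseline questionnaire score, so they do not, but the cross-reference needs tidying.

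Two limits also stand. Stratifying on age or pre-therapy would have balanced these scores only as far as they correlate with those factors. And complete pairs are unlikely at every visit; SAP 2.7.3 does not replace missing values.

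**Conclusion.** The point holds as a modest one. The plan lacks a baseline-adjusted between-arm estimate for FACIT-Fatigue and SF-36v2, although the baseline score is already collected. At about 12 unstratified patients per arm, adjustment would remove a chance component with a standard deviation of about 0.29, 0.20 or 0.12 SD at ρ = 0.3, 0.5 or 0.7. The variance would fall by 32%, 21% or 11%, with almost no gain at 0.8 to 0.9. These figures rest on assumed correlations, equal SDs, a linear baseline relation and complete pairs.

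The tempting stronger reading is that the planned change scores give a biased quality-of-life result, off by 0.12 to 0.29 SD. That is not supported. Randomisation keeps the contrast unbiased on average, and the figures describe the spread of a zero-mean shift already within the raw-change standard error. Nor would adjustment make the result precise, since its SE stays at about 0.30 to 0.40 SD for ρ from 0.7 down to 0.3.

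**What to change.** In SAP 2.11, for FACIT-Fatigue total and the SF-36v2 physical and mental component scores, add the baseline-adjusted mean difference between arms with its 95% CI. The model is the score at the visit on arm and baseline score, fitted at each planned visit (Weeks 1, 2, 4, 12, 26 and 52). Give no p-values and show the number of patients with data in each arm at each visit. Keep the raw summaries.

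Label the estimates descriptive and treatment-policy. Under protocol section 3 and Table 6-2, Arm B patients may start eltrombopag during follow-up. With three cycles at 14- or 28-day intervals, the third begins on Day 29 or Day 57, so a start can fall even before the Week 12 assessment. Limiting the table to early visits would therefore not avoid it.

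Add one sentence to SAP 2.7.2 saying that the logistic model does not apply to questionnaire scores. If the table is added after database lock, mark it post hoc.

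The cost is one small table per score from existing data. The downsides are the assumed linear baseline relation and 3 × 6 = 18 further descriptive estimates, none of which should be singled out because its interval excludes zero.

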#### 2.14 Interim analysis

Not applicable, no interim analysis is planned.

# 3 Sample size calculation

This trial is intended to estimate the difference in the rates of patients achieving a sustained response off treatment at Week 52.

The sample size calculation is based on the following assumptions:

- 1. Sustained response off treatment is achieved in 30% of the patients in the dexamethasone arm and 65% in the eltrombopag + dexamethasone arm
- 2. Randomization is allocated in a 1:1 ratio (eltrombopag + dexamethasone: dexamethasone)
- 4. A two-sided 5% level of significance will be applied.
- 5. The study will have 90% power under the stated assumptions for the primary endpoint.

Based on these assumptions, a total of 47 patients in each treatment arm would need to be randomized. More conservative scenarios based on lower treatment effects and 50 patients per group, assuming rates of 30 versus 60% would lead to a power of 81%, and 30 versus 55% would still allow for a power of 64%, whereas the radius of the respective confidence interval would be between 0.20 and 0.21 based these scenarios.

To allow for some dropouts/protocol violations, a total of 106 patients is planned to be enrolled.

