Data analysis	v2) The primary endpoint is the proportion of patients with sustained response off treatment at 52 weeks. Sustained response off treatment is defined as: • reach platelet count ≥ 30×10 ⁹ /L and then maintain platelet counts ≥ 30 × 10 ⁹ /L after treatment discontinuation AND • maintain platelet count ≥ 30 × 10 ⁹ /L in the absence of bleeding events ≥ Grade 2 and without the use of any rescue therapy at all visits until Week 52. The primary analysis will be performed comparing the treatment groups with respect to the primary efficacy outcome, based on the Odds Ratio, in a Logistic Regression model with the factor treatment and cofactors ITP-directed pre-therapy (during 3 out of 7 days before randomization), screening platelet count and age (≤ vs. > 60 years). The odds ratio and its 95% confidence interval (CI) and p-value will be given. As a consequence of Amendment 3, all analyses will be interpreted in a purely		
Key words	descriptive manner. Eltrombopag, immune thrombocytopenia, ITP, corticosteroids		

1 Introduction

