# Document History – Changes compared to previous final version of SAP

Date	Time point	Reason for update	Outcome for update	Section and title impacted (Current)
23- OCT- 2019	Prior to FPFV	Creation of 1st draft version by CRO- Statistician	For review of Novartis MA / TS	NA
09- JAN- 2020	Prior to FPFV	Review by Sponsor	Second draft for finalization	NA
13- MRZ- 2020	Prior to FPFV	Finalization Version 1.0	NA	NA
18- JUN- 2020	Prior to FPFV	Version 2.0 after review of TFLs	Algorithm for "Eligibility of discontinuation of study medication" was added	5.5.1.2
			Duration of sustained response: "from start of study treatment until loss of response " correted analogously to CSP- Update	2.7.1
			Dry run (before unblinding the study team) to check the convergence of the primary logistic model including several covariates included	2.5.2
16- NOV- 2023	Prior to DBL	Version 3.0 due to CSP amendment No. 2 and 3; 1st and 2nd DRM	Adaption to CSP amendment no. 2 and no. 3. As well as decisions from the first and second Data Review Meeting regarding analysis. Agreement on SAP, version 3.0, prior to DBL, signature shortly after DBL	

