## 1 Introduction

This Statistical Analysis Plan (SAP) describes how the statistical analyses of this study will be implemented. Based on the tables/listings/figures (TFL) of resulting from this SAP the Clinical Study Report (CSR) will be written. The TFLs will be attached in section 14 of the CSR.

In addition this SAP describes which Patient Data Listings to be attached in section 16.2.1 of the CSR will be generated.

This SAP is not used for other analyses or other studies.

It is based on the Study Protocol (CSP), Version 00 (Original protocol) dated 27-AUG-2019 (content final) and was updated for the Protocol Amendments 1 to 3.

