The primary analysis will be performed comparing the treatment groups with respect to the primary efficacy outcome, based on the Odds Ratio, in a Logistic Regression model with the factor treatment and cofactors ITP-directed pre-therapy ("no" vs. "yes" during 3 days before randomization), screening platelet count (quantitative) and age ( $\leq$  vs. >60 yrs). The odds ratio and its 95% confidence interval (CI) and p-value will be given. The null hypothesis of equal odds will be rejected if the 2-sided p-value from the logistic regression model for the factor "treatment" is <0.05; however, superiority of eltrombopag in combination with a short course of dexamethasone will be claimed only if the direction is correct, i.e. if the odds of response are higher under eltrombopag plus a short course of high-dose dexamethasone compared to 1-3 cycles of dexamethasone monotherapy (ORB/A < 1)

In case the analysis result is revealed to be unstable / does not converge due to cells with too low numbers, the covariates age and ITP-directed pre-therapy may be removed, until valid results are seen. This will be checked during dry run preparation, i.e. before the data have been unblinded, to warrant avoidance of data-driven decision making. Furthermore, during this process, an analysis using an exact logistic regression model (StatXact) may be considered.

<sup>3 For pretreated patients the last platelet count before pre-treatment was started

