# 4 Change to protocol specified analyses

No change from protocol specified analysis was made.

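### SAP 3.0 claims to incorporate Amendment 3 but keeps 106 patients, 90% power and a p<0.05 superiority rule, and omits the amended size, power and descriptive-only status

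*SAP*

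**What the plan says.** SAP 3.0 is dated 16 November 2023. Its document history gives the reason for the version as "Adaption to CSP amendment no. 2 and no. 3", and section 1 says that it "was updated for the Protocol Amendments 1 to 3". Section 4 adds "No change from protocol specified analysis was made".

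The operative SAP text nevertheless reads as follows:

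- Section 1.1 (Study design): "A total of n=106 will be enrolled".
- Section 3 (Sample size calculation): 30% versus 65% response, two-sided 5% level, "The study will have 90% power under the stated assumptions for the primary endpoint", 47 per arm, 106 planned. The section ends there.
- Section 2.5.2: the null hypothesis is rejected if the two-sided p-value for treatment is below 0.05, and "superiority of eltrombopag in combination with a short course of dexamethasone will be claimed only if the direction is correct".

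Protocol version 03 says something different about the amended trial. Section 12.8.1 keeps the original calculation but adds beneath it that recruitment stops early with about 24 patients: "Based on the assumptions described, the resulting power will be ca. 24"%. It then says that all analyses will be purely descriptive. The Data analysis entry of the protocol summary says the same: "As a consequence of Amendment 3, all analyses will be interpreted in a purely" descriptive manner. Protocol section 12.4.2, however, still contains the same reject-and-claim rule as the SAP.

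**The concern.** The SAP presents itself as current with all three amendments, but the part of Amendment 3 that changes the size and inferential standing of the trial did not reach it. Other parts did. The endpoint list no longer has the follow-up beyond Week 52 that Amendment 3 removed, and the model uses the screening platelet count that Amendment 2 introduced. A reader would therefore assume the remaining text was reviewed and kept on purpose.

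SAP section 1 says the report tables are built from the SAP. Someone working from it finds a conditional instruction to reject the null and claim superiority, and a reader finds 90% power for a trial that has nothing like it. The rule also spreads. Sections 2.7.1 and 2.7.2 analyse three secondary response endpoints (overall response to Week 52, overall response by Week 4, complete response by Week 4) in the same way as the primary. At about 12 per arm, a result that crosses p<0.05 will tend to overstate the effect, so an open route to a superiority claim is undesirable.

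**Working it through.** **Inputs.** Response rates 0.30 and 0.65, 1:1 allocation, two-sided 5%, 90% power, 47 per arm (SAP section 3). Amended size about 24, taken as 12 per arm, which is the scenario in the Amendment 3 rationale.

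**1. Reproduce the plan's figure.** Let d = 0.35 and the mean rate be 0.475. Without continuity correction:

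n' = [1.96·√(2·0.475·0.525) + 1.2816·√(0.3·0.7 + 0.65·0.35)]² / 0.35² = (1.384 + 0.848)² / 0.1225 = 40.7

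With the correction:

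n = (n'/4)·[1 + √(1 + 4/(n'·d))]² = (40.7/4)·(1 + 1.132)² = 46.2, so 47 per arm, as stated.

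Continuity-corrected power is Φ{[d − 1/n − 1.96·√(2·0.475·0.525/n)] / √(0.4375/n)}, where 0.4375 = 0.21 + 0.2275. At n = 47:

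(0.3287 − 0.2019)/0.0965 = 1.31, so power is 90.6%.

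The side scenarios at 50 per arm also reproduce: 81.5% for 30% versus 60% (stated 81%) and 64.8% for 30% versus 55% (stated 64%). The original arithmetic is sound.

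**2. Same formula at the amended size.** At n = 12:

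(0.2667 − 0.3996)/0.1909 = −0.70, so power is 24.3%, the protocol's figure of about 24%.

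If the final count were 10 to 14 per arm (an assumption), power would run from 18.5% to 30.3%.

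**3. Sensitivity to the test.** Exact enumeration of all 169 possible tables at 12 per arm gives:

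| Test (unadjusted) | Power | Mean observed difference, given p<0.05 favouring the combination | Smallest significant difference |
|---|---|---|---|
| Fisher | 29.3% | 57 points | 42 points |
| Logistic Wald | 43.9% | 51 points | 42 points |
| Chi-square, uncorrected | 45.9% | 52 points | 33 points (0/12 vs 4/12) |

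The Wald row counts tables with a zero cell as not significant. The assumed true difference is 35 points. Overstatement given significance is therefore a tendency. With Fisher and Wald every significant result exceeds 35 points; with the uncorrected chi-square some do not.

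**4. Precision.** The half-width of the 95% interval for the rate difference is 1.96·√(0.4375/n), plus 1/n for the corrected version.

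- n = 12: 1.96·0.1909 = 0.37; corrected, 0.37 + 0.083 = 0.46.
- n = 47: 0.19; corrected, 0.21.

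The corrected form gives 0.206 and 0.207 for the plan's two 50-per-arm scenarios, which matches its stated 0.20 to 0.21.

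For the odds ratio, (0.65/0.35)/(0.30/0.70) = 4.33 in favour of the combination. The plan's B/A form is the reciprocal, 0.23. With expected counts of 7.8 and 3.6 responders out of 12, the standard error of the log odds ratio is √(1/7.8 + 1/4.2 + 1/3.6 + 1/8.4) = 0.874. The 95% interval is 0.78 to 24.0. At 47 per arm it would be 1.82 to 10.3.

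**The case against.** The best defence has four parts.

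First, the 90% is an item in a list of design assumptions, and the current protocol keeps the same list. It is a planning input, not a report of the amended trial's power. That is fair, and the figure is correct for the original plan. But the protocol adds the Amendment 3 update under the list and the SAP does not. The SAP's enrolment statement in section 1.1 cannot be read as a design input at all.

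Second, the p<0.05 rule is not specific to the SAP, because protocol section 12.4.2 has it almost word for word. On that element the SAP's statement that nothing changed is accurate. This stands: the rule is a conflict inside the protocol that the SAP inherits. The difference is that the protocol switches the rule off in its summary and in section 12.8.1, whereas the SAP never does. The SAP's own descriptive wording for the primary endpoint covers supportive and subgroup displays, not the primary test.

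Third, the protocol governs, and the odds ratio, interval and p-value are produced either way, so only the wording of the conclusion is at stake. This is largely true and limits the severity. It does not make the SAP text right.

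Fourth, the power and interval illustrations are unadjusted, while the planned model has three cofactors and may be reduced or exact. That is correct. They show scale and do not predict the adjusted result, but no method tried comes near 90%.

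**Conclusion.** The concern holds. SAP 3.0 states a sample size and power that the amended trial does not have, and a decision rule that Amendment 3 withdrew in substance. It carries none of the three statements that replaced them. Under the plan's own assumptions (30% versus 65%, two-sided 5%, continuity-corrected), power falls from 90.6% at 47 per arm to 24.3% at 12. Across the unadjusted exact calculations it is at most about 46%. The fault is outdated and omitted text, not a calculation error. Read together, the documents make the controlling instruction descriptive, so this should be fixed but does not invalidate the analysis. The figures assume 12 per arm; the documents say only about 24 in total.

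**What to change.** 1. In SAP sections 1.1 and 3, keep 106, 47 per arm and 90% but label them as the original plan. Add the Amendment 3 figures: about 24 patients, about 24% power, and an expected 95% half-width for the rate difference of about 0.37 (0.46 with the continuity correction).
2. In SAP section 2.5.2 and protocol section 12.4.2, remove the sentences that reject the null and claim superiority. Report the response rates, their difference and the odds ratio with 95% confidence intervals, and label any p-value as descriptive. The interval for the difference is an addition, but it fits the aim stated in SAP section 3 of estimating the difference in rates.
3. Add one sentence to the SAP: under Amendment 3 all analyses, including the secondary endpoints analysed like the primary, are purely descriptive and no superiority claim will be made.
4. If protocol section 12.4.2 is left as it is, state in the SAP that protocol section 12.8.1 governs over it.

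The cost is a few lines, with no patients, no new data and no change of model. Rewording protocol section 12.4.2 would need a written amendment under protocol section 14.1; item 4 avoids that. The SAP history says version 3.0 was agreed before database lock and signed shortly after, so a change made after lock should be documented as such. The only loss is a superiority claim that Amendment 3 already gave up.
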